4.1 Introduction

Data processing, tabulation of descriptive statistics, and graphical representations will be performed primarily using SAS (release 9.4 or higher). If the use of other software is warranted, the final statistical methodology report will detail what software was used for what purposes.

Continuous (quantitative) variable summaries will include the number of patients (n) with non-missing values, the number of missing values, mean, standard deviation (SD), median, minimum, and maximum, unless otherwise specified.

Categorical (qualitative) variable summaries will include the frequency and percentage of patients who are in the particular category for each possible value. In general, the denominator for the percentage calculation will be based upon the total number of patients in the study population, unless otherwise specified.

The number of missing values will be calculated as difference between the total number of patients in the study population and the number of non-missing values.

The minimum and maximum will be reported with the same degree of precision (i.e. the same number of decimal places) as the observed data. Measures of location (mean and median) will be reported to 1 degree of precision more than the observed data and measures of spread (SD) will be reported to 2 degrees of precision more than the observed data.

Percentages will be presented to 1 decimal place, unless otherwise specified.

4.2 Interim Analysis, Data Review

4.2.1 Interim analysis

No formal interim analysis will be conducted.

4.2.2 Data review

No data review meeting will take place. After database lock, descriptive statistical outputs will be created.

5. Analysis Populations

The following analysis sets will be used for the statistical analysis:

Enrolled

- All patients from GWND18064 lead-in trial enrolled in GWND19002 trial.

Safety Analysis Set

- All patients who receive at least 1 dose of IMP in the GWND19002 trial will be included. Only patients for whom it has been confirmed that they did not take any IMP during the GWND19002 trial will be excluded from this safety analysis set. This analysis set will be used to report all statistical analysis.

Analysis sets will be identified during the conduct of statistical analysis after database lock.

6. General Issues for Statistical Analysis

All data collected in the study will be listed, ordered by site, patient number and, where applicable, chronological order of the assessment. Visit date is not needed to be included in the listings, day numbers will be included where appropriate.

Other derived variables (e.g. change from baseline values) that are calculated for analysis purposes or to aid interpretation of the data will be included in the data listings.

6.1 Statistical Definitions and Algorithms

6.1.1 Conventions for treatment/visit naming

In all tables, listings and figures, the treatment arms will be referred to and labelled as per [Table 2](#).

Table 2 Study treatments

Endpoint	RCT Treatment	Actual Treatment	Protocol/Annex	Treatment Label (Table column/Figure legend)	Sorting order in listings, column order in tables
All	Double-Blind Treatment GWP42003-P different dosing	GWP42003-P, at different dosing	Enrolled under Protocol	Double Blind Treatment: GWP42003-P Enrolled Under Protocol	1
All	Double-Blind Treatment GWP42003-P different dosing	GWP42003-P, at different dosing	Enrolled under Annex	Double Blind Treatment: GWP42003-P Enrolled Under Annex	2
All	Double-Blind Treatment Placebo different dosing	GWP42003-P, at different dosing	Enrolled under Protocol	Double Blind Treatment: Placebo Enrolled Under Protocol	3
All	Double-Blind Treatment Placebo different dosing	GWP42003-P, at different dosing	Enrolled under Annex	Double Blind Treatment: Placebo Enrolled Under Annex	4

In all tables, listings and figures, the study visits will be referred to and labelled as per [Table 3](#).

Table 3 Study Visits

Actual Visit	Visit Label
Baseline (last record before 1 st IMP administration during lead-in trial)	RCT Baseline
Baseline (Assessment at extension Visit 1)	OLE Baseline
Visit 1: Day 1	Day 1
Visit 2: Day 8 Telephone Call	Day 8 TC
Visit 3: Day 15 Telephone Call	Day 15 TC
Visit 4: Day 29	Day 29
Visit 5: Day 57	Day 57
Visit 6: Day 85	Day 85
Visit 7: Day 141	Day 141
Visit 8: Day 197	Day 197
Visit 9: Day 281	Day 281
Visit 10: Day 365	Day 365
Visit 12: Day 547	Day 547
Visit 14: Day 729 or withdrawal	End of Treatment
Visit 15: Day 739 (end of taper)	End of Taper
Visit 16: Day 767	Follow-up

No derivation will be used for visits; data will be tabulated and listed according to the visit it was recorded under in eCRF.

6.1.2 Baseline

For all endpoints, two baselines will be defined:

- the last non-missing observation recorded prior to the first drug administration during GWND18064 lead-in trial will be used as the RCT baseline
- The value reported at Visit 1 during OLE study will be used as the OLE baseline

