2.2.1.2 Secondary Efficacy Endpoints

The following will be assessed by evaluating changes relative to the prerandomization baseline of the GWND18064 lead-in trial:

- RSBQ
- CGI-I
- CGI-S.
- MBA-9.
- CSHQ.

Same analyses will be performed compared to OLE baseline.

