8.1 Rett Syndrome Behaviour Questionnaire (RSBQ)

The RSBQ is a caregiver-completed questionnaire that measures the frequency of current disease characteristics (45 items) that may or may not apply to the patient. Each item is rated on a 3-point numerical scale, where all items except for item 31 (“Uses eye gaze to convey feelings, needs and wishes”) is scored as follows: 0 indicating an item that is ‘not true as far as you know’, 1 indicating an item is ‘somewhat or sometimes true’, and 2 indicating an item that is ‘very true or often true’. Item 31 is to be reverse scored, where 0 indicates that this item is ‘very true or often true’, 1 indicating that this item is ‘somewhat or sometimes true’, and 2 indicating that this item is ‘not true as far as you know’. The total maximum score is 90 and higher total scores represent greater severity.

The RSBQ score and its change from baseline (RCT Baseline and OLE Baseline) will be summarized on a numerical scale by visit.

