8.3 Caregiver Global Impression of Severity (CGI-S)

The CGI-S is a 7-point scale that requires the clinician to rate the severity of the patient's illness at the time of assessment, relative to the clinician's experience with patients who have the same diagnosis. Considering total clinical experience, a patient will be assessed on severity of illness at the time of rating. This is rated as: 1 = normal, not at all ill; 2 = borderline ill; 3 = mildly ill; 4 = moderately ill; 5 = markedly ill; 6 = severely ill; or 7 = extremely ill.

CGI-S scores and their change from baseline (RCT baseline and OLE baseline) will be summarized by treatment and visit. Frequency table will be created for CGI-S categories by treatment and visit.

8.4 9-items Motor Behavioral Assessment (MBA-9)

The MBA-9 scale is completed by the investigator and addresses core symptoms of RTT. MBA-9 was derived from the full MBA scale (37 RTT symptoms) by selecting the items that are deemed to be amenable to change and that reflect areas of meaningful clinical change. The severity of current symptoms is rated on a 5-point numerical scale; 0 = normal or never; 1 = mild or rare; 2 = moderate or occasional; 3 = marked or frequent; 4 = very severe or constant. The MBA-9 score is calculated by summing the scores of the individual items. The maximum score is 36 and higher scores represent greater severity.

MBA-9 scores and their change from baseline (RCT baseline and OLE baseline) will be summarized by visit.

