8.4.1 Children's Sleep Habit Questionnaire (CSHQ)

The CSHQ includes a total sleep disturbance score and 8 sleep subscales: bedtime resistance, sleep onset delay, sleep duration, sleep anxiety, night wakings, parasomnias, sleep disordered breathing and daytime sleepiness. The items included in each subscale are presented in [Table 5](#).

Table 4 CSHQ Subscales

Subscale	Items Included
Bedtime resistance	1*, 3*, 4, 5, 6, 8
Sleep onset delay	2*
Sleep duration	9, 10*, 11*
Sleep anxiety	5, 7, 8, 21
Night wakings	16, 24, 25
Parasomnias	12, 13, 14, 15, 17, 22, 23
Sleep disordered breathing	18, 19, 20
Daytime sleepiness	26*, 27, 28, 29, 30, 31, 32, 33

* These items are to be reverse scored.

The responses to each item of the CSHQ are to be scored as Usually=3, Sometimes=2, Rarely=1, except for the items marked with * in [Table 5](#), which are considered to be “desirable” sleep behaviors and are therefore reverse scored. Items 32 and 33 are scored 1 for “not sleepy”, 2 for

“very sleepy”, 3 for “falls asleep”.

CSHQ scores and CSHQ subscale scores along with their change from baseline (RCT baseline and OLE baseline) will be summarized by visit.

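### The SAP takes OLE baseline only from OLE Visit 1, but none of the seven scales to be compared with it is scheduled at that visit for patients enrolled under the main protocol

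*SAP*

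**What the plan says.** SAP 6.1.2 sets two baselines for every endpoint. The RCT baseline looks back: it is the last non-missing observation before the first dose in the lead-in trial. The OLE baseline does not: "The value reported at Visit 1 during OLE study will be used as the OLE baseline". Table 3 in SAP 6.1.1 labels it the same way, "Baseline (Assessment at extension Visit 1", and the text under that table adds: "No derivation will be used for visits; data will be tabulated and listed according to the visit it was recorded under in eCRF".

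The OLE baseline is used widely. SAP 2.2.1.2 says of the secondary endpoints: "Same analyses will be performed compared to OLE baseline". Section 8 then writes the change score out scale by scale, for example:

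- SAP 8.1: "The RSBQ score and its change from baseline (RCT Baseline and OLE Baseline) will be summarized on a numerical scale by visit"
- SAP 8.3: "CGI-S scores and their change from baseline (RCT baseline and OLE baseline) will be summarized by treatment and visit"
- SAP 8.4: "MBA-9 scores and their change from baseline (RCT baseline and OLE baseline) will be summarized by visit"
- SAP 8.4.1: "CSHQ scores and CSHQ subscale scores along with their change from baseline (RCT baseline and OLE baseline) will be summarized by visit"

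SAP 8.5.1 (SF-36), 8.5.2 (CHQ-PF50) and 8.5.4 (Caregiver Assessment of Rett Symptoms) plan the same. SAP 9.5 states that the protocol intended only the RCT-baseline comparison and that the OLE-baseline comparison is an addition of the SAP.

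**The concern.** A change from OLE baseline needs a score at OLE Visit 1. If the schedule does not ask for one, and the SAP offers no substitute, the change cannot be formed for patients enrolled under the main protocol.

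This comparison is the one that isolates change on open-label drug in patients who had placebo in the RCT, since change from RCT baseline mixes the blinded and open-label periods. If only annex patients contribute, the combined summary describes a selected group: those whose RCT participation was disrupted, or who were withdrawn by the sponsor's decision. The n and missing counts required by SAP 4.1 would show the gap but not fill it. SAP 4.2.2 plans no data review meeting and produces outputs after database lock, so the gap might not be noticed until then.

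**Working it through.** No sample-size or power figure is involved. The check sets the planned change scores against the visit schedule.

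**Step 1: which scales.** Section 8 writes out change from OLE baseline for seven scales. CGI-I is not counted because SAP 8.2 summarises the score alone. The Hospital Services Use Questionnaire is not counted because SAP 8.5.3 only lists it.

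**Step 2: what is scheduled at OLE Visit 1 under the main protocol.** Protocol V2 9.1.1.1 has three Visit 1 lists: all patients; entry on a different date from RCT Visit 9; and entry more than 28 days after RCT Visit 9. None contains any of the seven scales. Protocol V2 Appendix 1 and SAP Table 1 agree.

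**Step 3: where the scales first appear** (same two schedules):

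| Scale | Scheduled OLE visits | Number | First OLE value |
|---|---|---|---|
| RSBQ | 4, 5, 6, 7, 8, 10, 14 | 7 | Day 29 |
| CGI-S | 4, 5, 6, 7, 8, 10, 14 | 7 | Day 29 |
| Caregiver Assessment | 4, 5, 6, 7, 8, 10, 14 | 7 | Day 29 |
| MBA-9 | 6, 8, 10, 14 | 4 | Day 85 |
| CSHQ | 6, 8, 10, 14 | 4 | Day 85 |
| SF-36 | 8, 10, 14 | 3 | Day 197 |
| CHQ-PF50 | 8, 10, 14 | 3 | Day 197 |

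OLE dosing starts on Day 1, so every first value is on drug.

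**Step 4: coverage by entry route.** The annex adds all seven scales at Visit 1. Annex V1 section 3.2.1 does so for all its entrants; Annex V2 section 3.2.1 only for those enrolling after RCT Visit 11.

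| Route | Scales scheduled at OLE Visit 1 |
|---|---|
| Main protocol, any timing | 0 of 7 |
| Annex V2, by RCT Visit 11 | 0 of 7 |
| Annex V2, after RCT Visit 11 | 7 of 7 |
| Annex V1, any timing | 7 of 7 |

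**Step 5: size in the planned tables.** Scale-by-visit change summaries per Table 2 column: 3×7 + 2×4 + 2×3 = 21 + 8 + 6 = 35. Check by visit (4, 5, 6, 7, 8, 10, 14): 3 + 3 + 5 + 3 + 7 + 7 + 7 = 35. Over four columns: 4×35 = 140. In the two protocol-enrolled columns: 2×35 = 70 with no scheduled OLE baseline. Subscales are not counted.

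**Step 6: safety measures, on the schedule only.** In SAP Table 1, laboratory tests, ECG and weight are required at Visit 1 only if it falls more than 28 days after RCT Visit 9 (footnote f), and vital signs only if it is not on the same day (footnote g). Of these four, a protocol entrant has 0 on same-day entry, 1 at 1–28 days and 4 beyond 28 days. SAP 9.2.1 and 9.3.1–9.3.3 list them at Visit 1 without conditions. SAP 9.3.6 does the same for menstruation, which Table 1 does not schedule there. SAP 9.2.1 also gives a different OLE baseline for repeated laboratory samples: the last value before Visit 1.

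**The case against.** The strongest reply is that RCT Visit 9 data were meant to serve. Same-day entry is the preferred route, footnotes f and g waive repeat measurements when Visit 9 is the same day or recent, and the unconditional Visit 1 lists in SAP 9 fit that reading. The no-derivation sentence in 6.1.1 can be read as a rule about visit labels, since Table 3 itself contains a derived RCT baseline. The eCRF is not available, so Visit 9 scores might be entered under OLE Visit 1.

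That may be the intent, but no passage says so. Even if 6.1.1 is only a labelling rule, 6.1.2 still names Visit 1 and gives no fallback. Two other possible rescues do not reach the problem. The wording in 9.2.1 covers repeated laboratory samples only. The carry-forward rule in 6.1.6.1 imputes missing items and does not say that RCT values fill an assessment never scheduled.

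Some points stand. The 70 of 140 is one scheduling fact multiplied over visits and columns; it is not a count of patients. The annex columns are not fully covered either, because Annex V2 entrants by RCT Visit 11 have none of the seven. The scales are secondary or exploratory and purely descriptive, and the comparison that the protocol promised is intact. A look-back rule also leaves two details to settle: patients who left the RCT without a Visit 9, and the Caregiver Assessment, which was a weekly diary in the RCT.

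**Conclusion.** The concern holds and should be fixed. Followed as written, the SAP gives protocol-enrolled patients no scheduled OLE baseline on any of the seven scales (0 of 7), which leaves 70 of 140 planned scale-by-visit change summaries without one and rests the combined summary on part of the annex group.

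This rests on the schedules as printed. The documents give neither patient numbers by entry route nor the RCT Visit 9 schedule, so the number of patients affected, and the number a look-back would recover, cannot be calculated. Some late visits may not occur because the trial stopped early. The safety figures in step 6 come from the schedule alone and conflict with the lists in SAP 9. Change from RCT baseline is not affected.

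**What to change.** - In SAP 6.1.2, Table 3 and 9.2.1, define OLE baseline as the last non-missing value on or before the first OLE dose: the OLE Visit 1 value if collected, otherwise the RCT end-of-treatment (Visit 9) value or a later RCT value, and never the RCT pre-dose baseline.
- Add an exception for this to the no-derivation sentence in 6.1.1.
- Set no look-back limit for the scales. Instead report, for each Table 2 column, the number with an OLE baseline and the gap from that value to the first OLE dose (same day, 1–28 days, more than 28 days).
- State what applies when a patient left the RCT without a Visit 9, and whether the Caregiver Assessment baseline is the last diary entry or a mean as in 8.5.4.
- Align the Visit 1 lists in 9.2.1 and 9.3.1–9.3.3 with footnotes f and g, and 9.3.6 with Table 1 and the annex.

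The cost is one definition, one exception sentence, some text alignment, and a merge with RCT data that the RCT baseline already requires. No visits are added. The drawbacks are that some baseline values will predate the first OLE dose, that values from the former active arm may have been taken on drug, and that coverage depends on what the RCT collected at Visit 9.

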6.1.3 Last Visit

The last visit for endpoints assessed at clinic visits is defined as the last scheduled visit at which a patient's last evaluation (up to Visit 15/end of treatment visit/any other last visit) is performed.

6.1.4 Day Numbering

The first day of treatment (Day 1) will be the date of Visit 1.

Any days prior to Day 1 will be numbered relative to this day and calculated as:

$$\text{Date} - (\text{Date of Day 1})$$

to give Day -1, -2, -3 etc.

Any days post Day 1 will be calculated as:

$$1 + \text{Date} - (\text{Date of Day 1})$$

6.1.5 Multiple Comparisons

No multiple comparisons are planned as no inferential analysis are planned.

6.1.6 Handling of Dropouts or Missing Data

Every effort has been made to minimize missing data for this trial. The patient reported outcomes will be completed by the patient's primary caregiver on electronic devices. These assessments have been set up in such a way that the caregiver cannot proceed to the next question if they have not entered a response for the current question. In addition, on the off chance that the device does not function correctly, paper alternatives of the assessments are available.

6.1.6.1 Handling of Missing Data for Efficacy Endpoint (Primary, Secondary and Exploratory)

If a questionnaire has subscales then the missing items in a subscale can be imputed as the mean of the non-missing items in that subscale, provided that at least half of the items in the subscale were answered. If more than half the items in the subscale are missing then the missing items will be imputed as LOCF.

If a questionnaire does not have subscales (eg MBA-9, CSHQ single item scale) the missing items will be imputed using LOCF.

6.1.6.1.1 SF-36

The SF-36 assessment will be scored by the QualityMetric Health Outcomes Scoring Software 5.0 (Maruish, 2011) which assumes that the response to a missing item in a particular scale is the same as the mean of the responses to the scale's answered items. This approach cannot be used to estimate item responses on the physical functioning scale due to the hierarchical nature of the items included in this scale. If items on the physical functioning scale are missing, the QualityMetric Health Outcomes Scoring Software v5.0 estimates the PF score using item response theory. If any SF-36 is logged as completed by an alternative caregiver, it will be counted as missing.

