9.2.12 Questionnaires and Assessments Completed at Scheduled Visits

Caregiver questionnaires should be completed by the identified caregiver, nominated at Visit 1 of the RCT. The same person should answer/complete the questionnaires/assessments in order to maintain consistency. Questionnaires should be completed during the scheduled visits. The nominated caregiver must have given consent to complete the QoL questionnaires prior to the completion of the questionnaires.

To ensure consistency, investigator-completed questionnaires should be completed for each patient by the same investigator throughout the trial. Investigators must have completed the sponsor-specified training for each questionnaire before any questionnaires are completed.

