6.1.6.1.2 CHQ-PF50

[Appendix 5](#) describes the methods of handling missing data for the CHQ-PF50 health scales.

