8.5.2 Patient Quality of Life Questionnaire

This instrument is a well-validated general QoL measure in pediatric populations with chronic illness. It measures QoL of the child and the family by parent or child report. The caregiver will be asked to complete the questionnaire on behalf of the patient. The CHQ-PF50 covers multidimensional health concepts including Physical Functioning, Role/Social Limitations–Emotional/Behavioral, Role/Social Limitations– Physical, Behavior, Mental Health, Self-Esteem, General Health , Bodily Pain, Family Activities, Parent Impact–Time, Parent Impact–Emotional, and Family Cohesion. Scores for specific items and subscales, as well as a standardized physical summary (PhS) score and a standardized psychosocial summary (PsS) score, can be calculated from the CHQ-PF50 questionnaire. Scores are based on a 0 to 100 scale and higher scores indicate better quality of life.

Table 7 presents the items included in each health concept.

Table 6 CHQ-PF50 Health Concepts

Health Concept	Items Included
Global health item	1.1
Physical functioning	2.1 (a to f)
Role/social limitations due to emotional/behavioral difficulties	3.1 (a to c)
Role/social limitations due to physical health	3.2 (a to b)
Bodily pain and discomfort	4.1 and 4.2
Behavior	5.1 (a to e) and 5.2
Global behavior item	5.2
Mental health	6.1 (a to e)
Self esteem	7.1 (a to f)
General health perceptions	8.1 (a to e) and 1.1
Change in health item	8.2
Emotional impact on parent	9.1 (a to c)
Time impact on parent	9.2 (a to c)
Family activities	9.3 (a to f)
Family cohesion item	9.4

Details regarding the scoring of the health concepts of CHQ-PF50 and of the PhS and PsS can be found in [Appendix 5](#). All of the health concepts and scales included in CHQ-PF50, except for the

change in health item are continuous.

CHQ-PF50 standardized scores (as per [Appendix 5](#)) CHQ-PF50 subscale scores, PhS and PsS scores along with their change from baseline (RCT Baseline and OLE Baseline) will be summarized by visit.

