Much better now than 1 year ago	1	5
Somewhat better now than 1 year ago	2	4
About the same now than 1 year ago	3	3
Somewhat worse now than 1 year ago	4	2
Much worse now than 1 year ago	5	1

This is a categorical scale and thus no transformation is necessary.

Emotional Impact on Parent

This scale includes items 9.1 (a to c) which are to be reverse scored in accordance with [Table 21](#).

Table 21 Scoring of Emotional Impact on Parent

Response	Precoded Item Values	Final Item Values
Not at all	1	5
A little bit	2	4
Some	3	3
Quite a bit	4	2
A lot	5	1

The emotional impact on parent scale score is then calculated as follows:

1. If at least 2 of the items in this scale have been answered, the raw score is obtained by computing the mean of the responses, otherwise this scale is set to missing.
2. The raw score is then standardized so that it ranges from 0 to 100 as follows:

$$(\text{Raw score} - 1) / 4 \times 100$$

Time Impact on Parent

Items 9.2 (a to c) are included in the time impact on parent scale. The responses range from 1 to 4 where 1 corresponds to “Yes, limited a lot” and 4 corresponds to a response of “No, not limited”. If at least 2 items in this scale have been answered the raw score is calculated as the mean of the items. If less than 2 items have been answered the scale is set to missing.

Finally, the standardized score which ranges from 0 to 100 is calculated as

$$(\text{Raw score} - 1) / 3 \times 100$$

Family Activities

The family activities health concept is comprised of items 9.3 (a to f). The responses range from 1 to 5 where 1 represents the response “Very often” and 5 the response of “Never”. If at least 3 items in this scale the raw score is calculated as the mean of the responses, otherwise the scale is sent to missing.

The raw score is then standardized as:

$$(\text{Raw score} - 1) / 4 \times 100$$

Family Cohesion Item

The family cohesion health concept includes item 9.4 which is recoded using the rules outlined in [Table 22](#).

Table 22 Scoring of Family Cohesion Item

Response	Precoded Item Values	Final Item Values
Excellent	1	5
Very good	2	4.4
Good	3	3.4
Fair	4	2.2
Poor	5	1

The score is then transformed so that it ranges from 0 to 100 as follows:

$$(\text{Raw score} - 1) / 4 \times 100$$

Standardized Physical Summary and Standardized Psychosocial Summary

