The PhS and PsS scales are scored using norm-based methods based on data from the general U.S. population and six clinical samples of children. [Table 24](#) includes the sample means and standard deviations, as well as factor score coefficients, used to derive the PhS and PsS scale scores.

Table 24 Information Required for Scoring PhS and PsS Scales

CHQ-PF50 SCALE*	MEAN	SD	FACTOR SCORE COEFFICIENTS	
			PhS	PsS
PF	90.8525408	16.3826344	.37138	-.09243
RP	91.4951246	18.9079749	.34493	-.06973
GH	66.6958379	19.3564297	.29460	-.05547
BP	78.6833515	20.7355708	.27883	-.05514
REB	90.4013015	19.5067502	-.01178	.21155
PT	83.8816188	20.2901603	.09113	.16944
PE	73.9788476	21.406013	.06063	.19823
SE	79.2555314	17.8308361	-.09480	.24792
MH	77.2595806	13.6861999	-.08263	.25335
BE	72.3086051	17.1447913	-.12675	.27911

Note: PF = Physical Functioning; RP = Role/Social-Physical; GH = General Health Perceptions; BP = Bodily Pain; REB = Role/Social Emotional/Behavioral; PT = Parental Impact-Time; PE = Parental Impact-Emotional; SE = Self Esteem; MH = Mental Health; BE = Behavior

The steps used in calculating PsS and PhS are summarized below:

1. Calculate each of the CHQ-PF50 scales presented in Table and using the methods outlined in this appendix.
2. Each scale is then standardized using a z-score transformation as follows:

$$\frac{\text{scale score} - \text{mean of scale}}{\text{std deviation of scale}}$$

where the mean and standard deviation for each scale are obtained from [Table 24](#)

3. Calculate PhS and PsS as a weighted sum of each standardized scale, using the factor score coefficients from Table 24 as the weights for each item in each scale.
4. Transform each scale score to obtain t-score with a mean of 50 and standard deviation of 10 as follows:

$$\text{PhS} = \text{PhS weighted sum} \times 10 + 50$$

$$\text{PhS} = \text{PhS weighted sum} \times 10 + 50.$$

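### The SAP sets aside an SF-36 completed by an alternative caregiver but has no such rule for the CHQ-PF50 parent-impact scales, which also measure the respondent

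*SAP*

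**What the plan says.** Protocol V2 section 9.2.12 has the caregiver nominated at Visit 1 of the RCT complete the caregiver questionnaires: "The same person should answer/complete the questionnaires/assessments in order to maintain consistency". Inclusion criterion 6.1.3 asks for willingness and ability to keep one caregiver for all caregiver assessments, and SAP 6.1.6 describes completion by the primary caregiver.

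The SAP gives a data rule for departures from this in one place only, SAP 6.1.6.1.1: "If any SF-36 is logged as completed by an alternative caregiver, it will be counted as missing".

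For the CHQ-PF50, SAP 6.1.6.1.2 says only that Appendix 5 "describes the methods of handling missing data for the CHQ-PF50 health scales". Appendix 5 sets conditions on the number of items answered. The emotional-impact scale is scored on the condition "If at least 2 of the items in this scale have been answered". For the time-impact scale, "If less than 2 items have been answered the scale is set to missing". Neither condition asks who answered. SAP 8.5.2 says of the instrument, "It measures QoL of the child and the family by parent or child report", has the caregiver complete it for the patient, and summarises subscales, PhS and PsS as change from the RCT and OLE baselines by visit.

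**The concern.** The SF-36 rule has a clear rationale. The instrument measures the caregiver's own health, so a form from another caregiver describes another person and cannot be subtracted from the first caregiver's baseline. The same reasoning applies to CHQ-PF50 items 9.1 (a to c) and 9.2 (a to c), which ask about the emotional and time burden on the responding parent. Under the SAP as written, a second caregiver's form is scored, differenced against the first caregiver's baseline and summarised as change.

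The difference does not stay in the two subscales. Both are among the ten scales that form PhS and PsS, so a change of respondent also moves the headline patient quality-of-life scores. There is no concurrent control group against which such a shift would show. Protocol 13.6.5 has all observed data summarised, and SAP 7.2 lists protocol deviations without removing data for them, so inclusion is the default.

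**Working it through.** The documents state no figure on this point, so there is none to reproduce. The check is textual first, then an illustration from the SAP's own weights.

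**Where respondent rules appear**

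| Instrument | What it describes | Respondent rule in the SAP |
|---|---|---|
| SF-36 (6.1.6.1.1, 8.5.1) | the caregiver | yes, counted as missing |
| CHQ-PF50 emotional and time impact on parent (6.1.6.1.2, 8.5.2, Appendix 5) | the responding caregiver | none |
| CHQ-PF50, other scales | the child or the family | none |
| RSBQ, CSHQ, Caregiver Assessment (8.1, 8.4.1, 8.5.4) | the child, rated by proxy | none |

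The second row is the gap: like the SF-36, it measures the respondent, but no rule applies.

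**Inputs** (SAP Appendix 5, Table 24, the "factor score coefficients, used to derive the PhS and PsS scale scores")

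- Time impact (PT): SD 20.2901603; coefficient 0.09113 for PhS and 0.16944 for PsS.
- Emotional impact (PE): SD 21.406013; coefficient 0.06063 for PhS and 0.19823 for PsS.

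**Formula.** Each scale is divided by its SD, weighted and multiplied by 10, so

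change in summary score = 10 × Σ [coefficient × (difference in scale ÷ SD)].

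The last step of Appendix 5 prints the PhS line twice. I take the second line to be PsS with the same transformation.

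**Illustration 1: respondents differ by 20 points on both scales (about 1 SD)**

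- 20 ÷ 20.290 = 0.9857; 20 ÷ 21.406 = 0.9343.
- PsS: 10 × (0.9857 × 0.16944 + 0.9343 × 0.19823) = 10 × (0.1670 + 0.1852) = 3.5.
- PhS: 10 × (0.9857 × 0.09113 + 0.9343 × 0.06063) = 10 × (0.0898 + 0.0566) = 1.5.

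**Illustration 2: the new respondent answers one category differently on every item of both scales**

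- Time impact is scored 1 to 4, so one category is 100 ÷ 3 = 33.3 points. This moves PsS by 2.78 and PhS by 1.50.
- Emotional impact is scored 1 to 5, so one category is 100 ÷ 4 = 25 points. This moves PsS by 2.32 and PhS by 0.71.
- Together: PsS 5.10 and PhS 2.21.

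**Group level.** The share of patients whose respondent changes is not in the documents. Assume 2% to 20%, with every difference in the same direction, so that mean shift = share × per-patient shift:

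| Assumed share | Mean PsS shift, illustration 1 | Mean PsS shift, illustration 2 |
|---|---|---|
| 2% | 0.07 | 0.10 |
| 5% | 0.18 | 0.25 |
| 10% | 0.35 | 0.51 |
| 20% | 0.70 | 1.02 |

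If the differences run in both directions, the mean moves less and the effect is mainly extra spread.

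**The case against.** The best counter-argument is that conduct already controls this. Criterion 6.1.3 and section 9.2.12 ask for one caregiver, and a switch would be a departure from 9.2.12 that SAP 7.2 can list. That limits how often the problem arises, but neither document says what to do with the data when it does.

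A reader might infer from the SF-36 sentence that alternative completion is expected or likely. The documents do not support that. The sentence is a contingency. No switch rate is given, and SAP section 1 says the extension is stopped prematurely, so follow-up to Day 729 cannot be assumed. Under the main schedule the CHQ-PF50 is collected only at Visits 8, 10 and 14, plus Visit 1 for late entrants under the annex.

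A reader might also infer that RSBQ, CSHQ and the Caregiver Assessment share the defect. SAP 8.1 says, for instance, "The RSBQ score and its change from baseline (RCT Baseline and OLE Baseline) will be summarized on a numerical scale by visit", with no condition on the respondent. But these are proxy ratings of the same child: a new rater gives a less comparable observation of the same subject, so treating them differently from the SF-36 is defensible. A size can be put on the RSBQ effect only with assumed inputs. With SD 12 and between-caregiver agreement (ICC) of 0.6 to 0.9, 12 × √(2(1 − ICC)) gives 10.7 down to 5.4 points. Neither input is in the documents, and the result includes ordinary measurement error that same-rater change already contains.

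Finally, discarding PhS and PsS whenever the respondent changes would be heavy-handed. Only two of their ten scales measure the respondent, and in PhS those two have coefficients of 0.09113 and 0.06063, against 0.37138 for physical functioning. This objection stands, and it is why both versions should be shown.

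**Conclusion.** The concern holds for the two CHQ-PF50 parent-impact scales and, through them, for PhS and PsS. At a visit completed by another caregiver, the SAP as written reports a between-person difference as change from baseline. The 3.5 and 1.5 points are per-patient illustrations; they rest on an assumed 20-point difference in the same direction on both scales and on the corrected PsS line in Appendix 5. The mean shift depends on an unknown switch rate and stays at or below about 1 PsS point even at an assumed 20%, all in one direction and with the larger per-patient difference.

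The CHQ-PF50 is an exploratory endpoint, all summaries are descriptive, and the primary safety objective is untouched. For the proxy-rated instruments the documents support no more than an optional additional summary.

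**What to change.** In SAP 6.1.6.1.2, add that when a CHQ-PF50 is logged as completed by an alternative caregiver, the emotional-impact and time-impact on parent scales count as missing in the change-from-baseline summaries of those scales. State that the last-observation rule in 6.1.6.1 does not refill them. Present PhS and PsS twice: as planned, from all ten scales, and restricted to visits with the same respondent as at baseline.

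Keep the main RSBQ, CSHQ and Caregiver Assessment summaries. Where the respondent is recorded, a same-respondent change-from-baseline summary may be added.

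The cost is a few sentences and a rerun of existing tables, with slightly fewer parent-impact values. The respondent must be available for the CHQ-PF50, including at RCT baseline; the documents mention logging only for the SF-36, so this needs checking first. The rule is best written before database lock: SAP 4.2.2 plans no data review meeting, and SAP 6.1.8 says the SAP will not be amended for additional derived variables unrelated to the primary or secondary endpoints, so a later exclusion for this exploratory instrument could be an undocumented choice.
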